## **E. METHODS**

### **1.0 Study Design**

#### **1.1 Overview of study design**

Following finalization of the Peer Interventionist training materials (described below in section 3.0), a pilot efficacy trial will be completed. This pilot study is a randomized controlled intent-to-treat (ITT) clinical trial. Potential participants will be recruited through various methods, which include but are not limited to advertisements, flyers, and word-of-mouth. Approximately eighty eligible participants will be randomized in a 1:1 ratio to the control condition (Information and NARCAN® Nasal Spray kit) or to the experimental condition (TTIP-PRO in addition to the elements provided in the control condition). All participants will complete a follow-up phone call approximately 3-weeks post-randomization, during which process measures will be completed, and in-person visits at approximately 3, 6-, and 12-months following enrollment.

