**Table 1. Overview of Study Assessments and Procedures for Study Participants**

Assessment/Procedure	Scr/Base/ Random	TTIP-PRO Intervention	3 WK FU call	3 Mo FU visit	6 Mo FU visit	12 Mo FU visit
Completed by	ASD RA	Peer Interventionist	ASD RA	ASD RA	ASD RA	ASD RA
Screening Assessments						
Informed consent	X					
Releases of information	X					
Demographics	X					
NIDA modified ASSIST	X					
Efficacy Measures						
MAT Entry Tracking				X	X	X
Opioid Overdose Tracking				X	X	X
Urine drug screen	X			X	X	X
Time line follow-back	X			X	X	X
Safety Measures						
Adverse Events			X	X	X	X
Process Measures						
HOPI			X			
OOTAS	X		X			
Barriers to Treatment	X		X			
Thoughts about abstinence	X		X			
Other Assessments						
Locator Information Form	X			X	X	
PORS	X					X
Utilization of NARCAN®				X	X	X
Interventions						
Provision of OOD and MAT information and NARCAN® Nasal Spray kit (all participants)	X					
TTIP-PRO Intervention		~ 2 weeks post-enroll				
Compensation	\$50		\$20	\$50	\$50	\$50

[figure not shown]

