### 5.2 Data Analysis

All analyses will be completed on the ITT sample using SAS (SAS Institute, Inc.). Statistical tests will be conducted at a 5% Type I error rate (two-sided) for all measures. It has been recommended that effect sizes be provided rather than using the Bonferroni procedure to adjust for multiple-comparisons; thus, effect sizes and 95% confidence intervals (CI's) will be computed for each treatment effect. For each efficacy analysis, demographic/baseline characteristics and length of time since last OOD will be selected for inclusion in the model using the corrected Akaike Information Criterion (AICC) as the optimizing criterion. For missing data, multiple imputation methods will be used and the resulting model compared to the non-imputed model. **Participant Analyses**-The primary hypothesis, that a significantly greater proportion of TTIP-PRO, relative to control, participants will enter MAT within 12-month follow-up will be tested using a logistic regression (a generalized linear model with a logistic link). Secondary analyses. The key secondary hypothesis, that a significantly lower proportion of TTIP-PRO, relative to control, participants will have a recurring OOD within 12-month follow-up will be tested using a logistic regression (a generalized linear model with a logistic link). The secondary hypothesis that TTIP-PRO, relative to control, participants will have a significantly greater reduction in illicit opioid use will be tested using two outcomes, one based on self-report and the other on UDS results. The proportion of self-reported use days will be treated as a binomial variable and regressed using logistic mixed model regression (random-intercept generalized mixed-model regression with a logistic link function). UDS results (positive for illicit opioids vs. not positive), will be treated as a binary variable which will also be regressed using logistic mixed-model regression. For both outcomes, the effects of interest will be treatment and treatment-by-time interaction.

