E2 – Testing the conceptual model of TTIP-PRO’s mechanisms of change. The purpose of the analyses described here is to explore the degree to which our conceptual model is consistent with the obtained study results. Using all ITT data, we will perform mediation analysis (empirically estimating 95% confidence intervals via bootstrapping) to test three mediation relationships: 1. fear-of-treatment, expected-success, and desire-to-quit as joint mediators of the effect of TTIP-PRO on engagement-in-MAT, 2. desire-to-quit, expected-success, and engagement-in-MAT as joint mediators of the effect of TTIP-PRO on level-of-opioid-use, and 3. knowledge-of-opioid-overdose and level-of-opioid-use as joint mediators of the effect of TTIP-PRO on whether there is an opioid overdose recurrence. We will test whether helpfulness-of-the-intervention (HOPI) respectively moderates the effects of fear-of-treatment, expected-success, desire-to-quit, and knowledge-of-opioid-overdose. We will perform logistic regression when engagement-in-MAT and overdose-recurrence are outcomes and logistic mixed-model regression when opioid use is the outcome.

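### The E2 mediation plan does not specify adjustment for the mediators' own baseline scores, which the trial collects; a minor, cheap improvement to an exploratory analysis

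*Combined protocol and SAP*

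**What the plan says.** Section 5.2, E2, gives the method as "Using all ITT data, we will perform mediation analysis (empirically estimating 95% confidence intervals via bootstrapping) to test three mediation relationships". The first model takes "fear-of-treatment, expected-success, and desire-to-quit as joint mediators of the effect of TTIP-PRO on engagement-in-MAT". The second has desire to quit, expected success and MAT engagement as mediators of opioid use. The third has "knowledge-of-opioid-overdose and level-of-opioid-use as joint mediators of the effect of TTIP-PRO on whether there is an opioid overdose recurrence". The text names the regression types but no mediator time point, change score or covariate. The E2 text in the DSMP (Appendix B, III.3) describes these three models in the same way.

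Section 1.1 places the process measures at a "follow-up phone call approximately 3-weeks post-randomization, during which process measures will be completed". Table 1 marks the Barriers to Treatment, "Thoughts about abstinence" and OOTAS rows at screening/baseline and at the week-3 call, and nowhere else. The post-randomisation value of these four mediators can therefore only be the week-3 score, and each has a baseline counterpart.

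The one covariate rule, also in 5.2 and repeated in the DSMP, reads "For each efficacy analysis, demographic/baseline characteristics and length of time since last OOD will be selected for inclusion in the model", using AICC. It does not mention the baseline mediator scores.

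**The concern.** Randomisation protects the effect of arm on the mediator. It does not protect the association between the mediator and the outcome. A participant who already wanted to quit at enrolment will tend to score high at week 3 and may be more likely to enter MAT, whatever the call did. The baseline score is the most direct measure of that tendency that the trial holds, and usually the best predictor of the week-3 score. If it is left out, the mediator-to-outcome coefficient absorbs the stable trait, and the arm-to-mediator comparison is noisier than it needs to be.

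At stake is what E2 carries into the full-scale trial that this pilot prepares. A mechanism could be credited that TTIP-PRO does not work through.

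**Working it through.** The plan gives no effect size, power or correlation for E2, so there is no figure of its own to reproduce.

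**From the documents:** 80 participants, 1:1 (40 per arm); 62 if 78% complete 12 months (31 per arm); two-sided 5%; MAT entry of 12% in control against 39% (n=80) or 46% (n=62), as used in the power statement.

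**Assumed:** baseline to week-3 correlation ρ, effect of arm on the mediator (in SD), effect of the stable trait on MAT entry (log-OR per SD).

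**1. False mediation, trait measured with error.** Baseline score M0 and week-3 score M1 share a trait U, with ρ = 0.6. M1 is shifted by the arm effect. logit P(MAT) = −1.2 + c·U with c = 0.5 or 1.0 (24 to 27% entry), so the mediator has no causal effect. Mediation is declared when both paths have |z| > 1.96, a stand-in for the bootstrap interval. Each setting had 2,500 runs with one mediator.

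| Arm effect on mediator | n | Unadjusted | Baseline-adjusted |
|---|---|---|---|
| 0.6 SD | 62 | 14–39% | 9–17% |
| 0.6 SD | 80 | 23–58% | 9–23% |
| 0.3 SD | 62 and 80 | 3–20% | 3–11% |
| none | 62 and 80 | under 5% | under 5% |

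Ranges run over c. Repeat runs move most ends by up to about two or three percentage points. With no arm effect, the first path is significant only 5% of the time, which caps the joint rate.

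Adjusted error stays above 5% because one baseline score is an imperfect measure of U. Regressing U on M1 alone gives √ρ; on M1 and M0 together it gives √ρ/(1+ρ) for M1. The share of confounding left is 1/(1+ρ) = 1/1.6 = 0.625.

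**2. False mediation, baseline score itself the confounder.** This used an interval test of the product, 3,000 runs, N=80 and log-OR 1.0. At a 0.5 SD arm effect the rate is 20% (ρ=0.5) to 35% (ρ=0.7) unadjusted, against 3.0 to 3.7% adjusted. At 0.8 SD it is 35 to 65% against about 5%. With no arm effect it is 1.0 to 2.7% unadjusted. With log-OR 0.5 (ρ=0.7, 0.5 SD) it is 13% against 4%.

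**3. Precision of the arm-to-mediator path.** Detectable difference at 80% power = (1.960 + 0.842) × √(1−ρ²) × √(2/n per arm). For 40 per arm, unadjusted: 2.802 × 0.2236 = 0.63 SD.

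| | No baseline | ρ=0.3 | ρ=0.5 | ρ=0.7 |
|---|---|---|---|---|
| Detectable, 40/arm | 0.63 | 0.60 | 0.54 | 0.45 |
| Power at 0.5 SD, 40/arm | 61% | 65% | 73% | 88% |
| Detectable, 31/arm | 0.71 | 0.68 | 0.62 | 0.51 |
| Power at 0.5 SD, 31/arm | 50% | 54% | 62% | 79% |

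**4. Cost in the outcome model.** Expected MAT entries are 31 × 0.12 + 31 × 0.46 = 3.7 + 14.3 = 18.0, or 40 × 0.12 + 40 × 0.39 = 4.8 + 15.6 = 20.4. With three joint mediators, adding three baselines takes the model from 4 to 7 coefficients plus an intercept, or 18.0/7 = 2.6 to 20.4/7 = 2.9 events per coefficient. In a three-mediator simulation (assumed trait correlation 0.4), the median SE of the mediator-to-MAT coefficient rose from about 0.36 to 0.47 at n=62 (ratio 1.31) and from 0.32 to 0.40 at n=80 (ratio 1.25).

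**The case against.** **Silence is not exclusion.** A reader might infer that the plan has decided to use week-3 scores without baselines. It has not said so: E2 gives no time point or covariate list, week 3 is inferred from Table 1, and the conceptual-model figure was not available for this check. Nor does every mediator have a baseline value. MAT engagement has none, because current addiction treatment is an exclusion. This stands, and the point is limited to what E2 leaves unspecified.

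**The AICC rule may reach E2.** Section 1.4.1 describes Fear of Treatment and OOTAS as mediators of the intervention's efficacy. In a check of the set-up in step 1, AICC kept the baseline score in the mediator model in at least 99.9% of trials, so on that reading no precision is lost. It kept it in the outcome model in only 20 to 49%, so confounding would often remain.

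**The size depends on an arm effect.** A reader might infer that E2 will report a mechanism that does not exist. The documents do not support that. The risk arises only if TTIP-PRO moves the mediator. Section C reports knowledge rising from 69.9% to 93.6% correct, but in eight patients, pre-post, without control, and it reports no such change for the motivation scores.

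**E2 is exploratory.** Its stated aim is to "explore the degree to which our conceptual model is consistent with the obtained study results". This stands, and it limits the weight of the point.

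**Conclusion.** The gap is real and minor. E2 does not specify adjustment for baseline Fear of Treatment, desire to quit, expected success or OOTAS, and no other rule in the plan guarantees it. If TTIP-PRO shifts a mediator that has no effect of its own, unadjusted models declare mediation too often: about 14 to 58% against 9 to 23% with adjustment at a 0.6 SD shift. The gap is much smaller at 0.3 SD and immaterial with no shift. The precision gain is worthwhile at a correlation of 0.5 to 0.7 and slight near 0.3.

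These sizes rest on inputs that the documents do not give and on a single mediator. The direction holds in both confounding models; the exact percentages should not be quoted as properties of this trial. Adjustment reduces confounding without removing it. No primary or secondary conclusion is affected.

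**What to change.** In 5.2 E2 and in DSMP III.3 E2, state the following.

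- For each mediator measured at week 3 (BTI Fear of Treatment, TAA desire to quit, TAA expected success, OOTAS), its own baseline score enters both its mediator model and the outcome model, and is exempt from AICC selection.
- Where level of opioid use is the mediator (third model), adjust for baseline TLFB use days, unless baseline is already a time point in that model.
- No baseline term applies to MAT engagement.
- Fit the MAT-entry outcome model with a penalised likelihood, for example Firth logistic regression, and report the model without baseline scores as a sensitivity analysis.
- Say in the report that residual confounding of the mediator-to-outcome path remains possible.

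The cost is wording in two places, with no new data, visits or participants. The real downside is that the SE of the mediator-to-MAT coefficient rises by roughly a quarter to a third on about 18 to 20 events. That is why the penalised model and the sensitivity analysis belong in the same change.

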## **6.0 Study completion time**

An individual participant’s period of time for participation and study completion is approximately 12 months. For an individual Peer Interventionist, the time for participation and completion in the pilot trial is approximately 16 months, which includes the time needed for training and certification and for providing TTIP-PRO sessions during the approximately 14-month enrollment period. It is expected that two Peer Interventionists will help to develop the training materials and also participate in the pilot trial; their time of participation and study completion may take up to 24 months. The present project will take less than 3 years to complete.

## **F. HUMAN SUBJECTS**

A detailed data and safety monitoring plan (DSMP), which has been approved by the study sponsor (NIDA) is provided in Appendix B.

**Prisoner Status-** Due to the illegality of illicit opioid use, many potential participants are likely meet the definition of prisoner (e.g., being in jail or prison, detained in other facilitates as an alternative to criminal prosecution or incarceration, being on probation or parole, being under house arrest or electronic monitoring, etc.). This trial would, thus, be challenging to conduct without allowing the participation of individuals who meet the definition of a prisoner. All randomized participants will receive direct benefit from participating in this trial by receiving: 1) the NARCAN® Nasal Spray kit, which could save their lives if they experience another opioid overdose; 2) information about opioid overdose and substance abuse treatment. For individuals who are, or become during the course of their participation, prisoners, study participation will have no effect on the participant’s criminal case, release or parole from jail or prison, or probation case.

## **G. RISK/BENEFIT ASSESSMENT**

This project includes two types of participants: 1) the participants who may receive the TTIP-PRO intervention, referred to as participants, and 2) the participants who will serve as Peer Interventionists.

Risks associated with the TTIP-PRO intervention. TTIP-PRO consists of two parts: 1) an information packet which includes three reports (“Personal Overdose Risk Factors Report”; “Medication Assisted Treatment (MAT) Report”; and the “Opioid Overdose Information Report”) generated from the participant’s responses to two surveys and information about how to be access treatment at a UC ASD (UC Health/UCPC) MAT program; 2) a 20-minute telephone intervention delivered by Peer Interventionists. The Peer Interventionists interact with the study participants only on the phone, not in person, and, thus, physical safety is not a concern. The phone intervention may last up to 20 minutes during which the Peer Interventionist will answer the participant’s questions about the information packet reports, with the potential answers being highly scripted, and an exchange of information between the Peer Interventionist and participant about MAT.

Potential risks of TTIP-PRO for participants include: 1) breach of confidentiality and 2) improper administration of the intervention by the Peer Interventionist. The Peer Interventionists will be provided with the first name and phone number of the participants assigned to them in a secure manner. As part of their training, the Peer Interventionists will be instructed on methods for maintaining confidentiality. Several steps will be taken to ensure proper administration of the intervention. First, all Peer Interventionists must complete a 4-hour training and certification before being assigned study participants as described in section 3.3. Second, all interventions will be audio recorded and rated for adherence/fidelity using the same assessment as that used for certification. Any instance of falling below certification criteria will result in additional training or discontinuation from the trial depending on the nature of the problematic performance.

Potential risks of TTIP-PRO for Peer Interventionists include: 1) breach of confidentiality and 2) increased risk of relapse. In order to diminish the possibility of the participants discovering PHI about the Peer Interventionists, a study cell phone, rather than the Peer Interventionist’s personal cell phone will be used; this will avoid the potential for the participant obtaining the Peer Interventionist’s phone number and then using the number to determine information about the Peer Interventionist (i.e., name, address). The Peer Interventionists will be exposed to active users during the 20 minute telephone intervention. As noted above, for individuals early in recovery or struggling with recovery and/or other issues, interacting with active users could increase the risk of relapse. Our Peer Interventionist eligibility criteria are designed to select only those individuals whose recovery is sufficiently stable to mitigate this risk. The consent form will clearly delineate relapse as a potential risk. The potential Peer Interventionist will need to agree to an ongoing exchange of information between the research team and his/her treatment providers in order to monitor his/her clinical status. [name] and her research team are co-located with the clinic staff for the UC ASD MAT program and interact on a daily basis; the clinic staff will be instructed to inform the research team of any deterioration in the Peer Interventionist’s functioning. In the event of clinical deterioration, the clinic’s multi-disciplinary team will develop a treatment plan, which may include the Peer Interventionist’s discontinuation from study participation. Peer Interventionists will be compensated \$40 for completing training/certification, and \$20 for each participant for whom they provide the intervention. Peer Interventionists will not be compensated with cash, which could potentially be used to purchase illicit opioids but, rather, with a prepaid debit card.

Risks associated with study participation. Breach of confidentiality: As with any study, there is a potential risk of loss of confidentiality. To maintain confidentiality, study records and data will be stored in compliance with the International Conference on Harmonization (ICH) guidelines. Participant/Peer Interventionist records will be held confidential by the use of study codes in the study database, secure storage of any documents that have participant identifiers, and secure computing procedures for entering and transferring electronic data. No identifying information will be disclosed in reports, publications or presentations. Information collected for this study will be kept in a locked secure location accessible only to research staff and authorized personnel directly involved with this study. Finally, a Certificate of Confidentiality will be obtained for the study. Emotional Discomfort: The participants may experience some

emotional discomfort from answering sensitive and/or personal questions. Participants may experience embarrassment in answering questions about their knowledge of MAT and OOD. The participants/Peer Interventionists can choose to not answer questions that they find to be too uncomfortable and will be reminded that study participation is completely voluntary. NARCAN® Nasal Spray kit. This medication has a very favorable side-effects profile. However, there have been rare cases in which using naloxone to reverse an OOD has resulted in vomiting, sweating, shaking, tachycardia, elevated blood pressure, seizures, pulmonary edema, ventricular dysrhythmias, rapid pulmonary edema, and cardiac arrest.

Benefits. The results of the present pilot study are unlikely to have a direct substantial societal impact. However, promising pilot results would be used in support of a larger trial to test the efficacy of the TTIP-PRO in reducing the recurrence of opioid overdoses. Should that project yield promising results, the benefits to individuals and to society could be substantial. Both the study participants and the Peer Interventionists may directly benefit from study participation in that they will receive information about risks for overdose, the signs of overdose, how to respond to an overdose, and factors that can reduce the risk of an overdose. The study participants may also benefit from receiving a NARCAN® Nasal Spray kit. Consequently, the risk/benefit ratio is favorable and conduct of the research well justified.

## **H. PAYMENT**

Participants will also be reimbursed up to \$220 for their time and travel. Peer Interventionists will be provided with a study cell phone for use in delivering TTIP-PRO and for staying in contact with research staff regarding scheduled and completed interventions. Peer Interventionists will be compensated \$40 for completing training/certification, and \$20 for each participant for whom they provide the intervention. Payments will be provided via a prepaid debit card.

## **I. SUBJECT COSTS**

There are no subject costs for participating in this study.

## **J. CONSENT FORMS**

Attached

## Appendix A: Examples of TTIP-PRO-generated reports for fictional patient

### 1.0 Example of a “Personal Overdose Risk Factors Report” for a fictional heroin user

Personal Overdose Risk Factors Report

**Personal Overdose Risk Factors Report  
for Sam  
Based on a Survey Taken 02-20-2017**

**Disclaimer:**

You were asked about risk factors that are known to be related to increased risk for having an opioid overdose, but you may have other risk factors that we did not assess. This list of risk factors was generated from the answers that you provided.

Anyone who uses heroin is at risk for an overdose. Based on your answers, there are 11 factors that increase your risk above the risk of just using heroin. These factors include:

**Increasing the amount of heroin that you use to get high:**

When you use more heroin than you are used to, it becomes much easier to accidentally overdose by using more than your body can handle.

